3.4 Decoding Procedures

Participants with study ID's starting with A will be in the intervention group and those with study ID's starting with B will be in the comparison group. Participants with C at the start of the study ID will be excluded from analysis.

3.5 Duration

The trial, including pre and post-assessments and intervention delivery, will last approximately 45 to 50 minutes (one school period) of a single school day.

3.6 Discontinuation

If there is an unexpected emergency related or not related to the intervention at the trial location the trial will be discontinued

3.7 Product Accountability

This is not applicable.

3.8 Data Identification

This is not applicable.

4 Selection and Withdrawal of Participants

4.1 Inclusion Criteria

- Attend Muriel Clayton Middle School
- Be in grade 7 or 8
- Be enrolled in the standard Alberta grade 7 or 8 curriculum
- Provides implied consent
- Parent or guardian provides written consent
- Able to understand the language of the video

4.2 Exclusion Criteria

- Younger than 11 years old
- Older than 16 years old
- Does not provide implied consent
- The parent or guardian does not provide written consent
- Unable to understand the language of the video or questionnaire due to language barriers of developmental delay

4.3 Participant Withdrawal

If participants show distress or do not want to continue during the study they will be withdrawn from the study and school counselors and or teachers will be informed. Consequently, they will be taken to another room by the teachers. Once the envelopes have been handed in, participants cannot withdraw from the study.

4.4 Medication

N/A

4.5 Monitoring for Participant Compliance

Research assistants present in the rooms during the intervention will support participants in complying with the study procedures.

5 Assessment of Efficacy

5.1 Efficacy Parameters

Attitudes and perception regarding vaping and participant perception of intervention.

5.2 Method and Timing

The two adapted versions of the validated surveys assess attitudes and perceptions in relation to e-cigarette or "vaping" use. The students will be informed by their teachers prior to survey distribution that e-cigarette terminology and vaping are interchangeable. For both of the surveys, participants rate how much they agree with each statement (on a numbered scale between "*strongly disagree*" and "*strongly agree*") related to vaping/e-cigarette use (*e.g. "e-cigarettes are safer than smoking"*). To determine if there was any difference in attitudes, knowledge, or harm perceptions related to vaping before and after the intervention.

Demographic information collected in the personal information questionnaire will include age, gender, and grade. This information will be used to describe the sample recruited and assessed for variations between different groups. No other identifying personal information will be collected (name, contact information, etc.) and all results will be anonymous.

The *Video Survey* is a questionnaire adapted from a previous study (Hollis et al., 2022) asking students regarding their opinion of the intervention's effect on their vaping knowledge, usefulness to others, and overall knowledge about vaping following the intervention ². This information will be collected to determine how the intervention was perceived by the participants. Students will also be asked if they have vaped to inform on the effect of prior vape use on the perception of the intervention and efficacy and changing attitudes. Short answer questions asking participants what they liked and what they disliked in the intervention will also be included to inform future directions.

6 Assessment of Safety

6.1 Safety Parameters

Mental distress during and or following the intervention and evaluation, although this is unlikely.

6.2 Method and Timing

Research assistants and school staff will monitor participants during the study period and assess any potential mental distress.

6.3 Adverse Event Reporting

Adverse events will be reported in accordance with CHREB and Health Canada policies as well as any applicable Rocky View County School Board procedures.

6.4 Adverse Event Definitions

If participants are seen to be engaging in abnormal behavior compared to their regular behavior expected in schools or if participants themselves indicate that they are facing mental distress and or any other form of an adverse event.

6.5 Adverse Event Follow-up

Participant's condition following an adverse event will be followed up with school staff and if there is reason to believe the adverse event was caused by the intervention information will be gathered either by talking with the afflicted participant (if appropriate given the circumstances) and or the school staff and parents.

7 Statistical Plan

7.1 Statistical Methods

Data from questionnaires will be entered into an Excel spreadsheet by research assistants. A double entry will be performed to reduce the frequency of data entry errors. New variables will be created by taking the difference in the individual items and overall scores for KAS and EHI pre and post-intervention for each participant ^{20,21}. In order to ensure that higher scores reflect an increased likelihood of vape abuse, question 10 on the KAS will be reversed scored as a study showed that on this question vape non-users were more likely to score higher than users ²⁰. Descriptive statistics and graphics for participant demographic characteristics and questionnaire responses will be performed prior to primary analysis to detect errors in data, such as missing data and variables being outside of the plausible range. If errors are found they will be addressed. After this, the database will be locked.

Initially, to confirm the validity of creating a total score, we will confirm internal consistency using Crohnbach's alpha. We assume that internal consistency will be adequate and therefore describe an analysis of total scores on the scale in the remainder of this section.

The analysis will begin by describing sample characteristics. Following this, a primary analysis will be undertaken to evaluate the success of the intervention. Imbalances in randomization will be looked at using graphical methods and tables and will be adjusted using linear regressions if the distributional assumptions and the assumption of linearity

are met as assessed with a scatter plot. If the distributional assumptions are not met then quantile regression will be used. T-tests will be performed to assess if the intervention group had a significant change between pre and post-intervention compared to the comparison group on the KAS and EHI. If data is not normally distributed non-parametric tests will be used. The robustness of the primary analysis will be assessed by adjusting for other variables through linear regression models.

An exploratory analysis will be done and will involve using T-tests to determine if the individual item scores for the first 5 questions on the Video Survey are significantly different between the experimental and comparator groups. Mann-Whitney U test will also be used to determine if the two groups responded differently for questions 5 and 6 on the Video Survey.

An exploratory analysis will be undertaken to specifically explore if the intervention group had a significant change between pre and post intervention compared to the comparison group on the KAS questions 1, 3, and 7 and for the EHI questions 1, 2, 6, 7, 11, and 13. Further analysis looking at all individual items on the KAS, EHI, and video survey will be done to explore if the intervention group had a significant change between pre and post intervention and if the personal information collected impacts scores.

All analyses will be performed on Stata 18.

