3.1 Primary Study Endpoints/Secondary Endpoints

The primary endpoints are individual and aggregate item scores on the *Knowledge and attitudes regarding e-cigarette ingredients, safety, and addictive properties survey* (KAS) and *E-cigarette Harm Perception and Reduction Items* (EHI) post-intervention ^{20,21}. The secondary endpoints are the aggregate and item scores on the *Video Survey*.

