3.2 Study Design/Type

This is a pre/post-randomized control study design. Research assistants will collect data at Muriel Clayton Middle School and conduct the statistical analysis. There will be a comparison group that receives a vaping video intervention developed by the National Health Institute, and an experimental group receiving the intervention. Questionnaires will be used to collect data.

Classroom teachers will be given a script that they will use to introduce the study to the students of both groups using the study introduction script. Students will be informed that their responses will be completely anonymized to minimize the risk of social desirability bias. School teachers will help to identify any students who do not meet the inclusion criteria and they will be excluded from the analysis. Each student participating in the study will be given an envelope containing a unique study ID, Personal Information Questionnaire, Video Survey, information sheet describing the study, and a copy of each of the KAS and EHI. KAS and EHI in the envelopes will be labeled "1", signifying pre-intervention. Following the intervention participants will receive another copy of the KAS and EHI labeled "2", signifying post-intervention, which they will place in the envelope after completion. None of the forms will have any identifying information (outside of age, grade, and gender) and the school teachers will not review the data collected. Individuals present in the rooms will include one or more school staff, research assistants going in between rooms if there are more than two rooms, and the student participants. The students will complete the Personal Information Questionnaire, KAS and EHI, prior to watching the intervention video. Following the intervention they will be provided with another copy of the KAS and EHI along with the Video Survey. Once students have completed the questionnaires they will be asked to place everything back in the envelope and hand the envelope to the research assistant.

After completion of the assigned video and associated evaluations, students will be shown the other video. This will be done to ensure that no student is excluded from any of the benefits of either of the treatments.

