3.3 Randomization

Each classroom of grades 7 and 8 at Muriel Clayton Middle School will be divided into group A and B evenly. Research assistants will alternatively place students in groups A Ethics ID: REB23-1437 Date: 1/11/2024 Version: 8 and B based on software (e.g Excel) to produce a randomized sequence of A's and B's. After all students have been assigned they will proceed to their groups' assigned room and receive an envelope. The envelopes will contain the students study ID and will start with the letter A or B corresponding to their assigned group. All students in group A will complete the questionnaires, watch the intervention video, and then complete the same questionnaires immediately after the intervention. All students in group B will complete the questionnaires, experience the control condition (NIH video) and then complete the same questionnaires. The teacher will introduce the study prior to group assignment.

Students not meeting the inclusion criteria will be assigned group C. A set of envelopes with a "C" code will be prepared beforehand and distributed to group C students. These Group C students will follow the same procedure as group A but will be excluded from analysis.

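### Section 7.1 rests the primary comparison on a change-score t-test and lets the observed data choose covariates and method, although a fixed ANCOVA on the baseline score is available and more efficient

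*Protocol*

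**What the plan says.** Both questionnaires are taken before the video. Section 3.2 states: "The students will complete the Personal Information Questionnaire, KAS and EHI, prior to watching the intervention video". Section 3.1 names the post-intervention KAS and EHI scores, item by item and in aggregate, as primary endpoints.

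Section 7.1 then sets out the analysis:
- Outcome variable: "New variables will be created by taking the difference in the individual items and overall scores for KAS and EHI pre and post-intervention", computed per student.
- Test: "T-tests will be performed to assess if the intervention group had a significant change between pre and post-intervention". The contrast is with the other arm, for both scales.
- Covariates: "Imbalances in randomization will be looked at using graphical methods and tables and will be adjusted using linear regressions", provided that distributional assumptions and linearity look acceptable on a scatter plot; otherwise quantile regression is used. No covariate is named.
- Fallback for the t-test: "If data is not normally distributed non-parametric tests will be used". Neither a criterion nor a test is given for the primary scales.
- Robustness: linear regression on other variables, not listed.

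Section 3.3 describes allocation within class: "Each classroom of grades 7 and 8 at Muriel Clayton Middle School will be divided into group A and B evenly". Section 7.2 gives about 50 students per arm and detectable differences of 1.52 (KAS) and 3.58 (EHI) points at 80% power. Section 7.3 sets alpha at 0.05.

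**The concern.** Two things are at stake.

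The first is efficiency. A change score fixes the coefficient of the baseline score at 1, whereas ANCOVA estimates it. When the pre-post correlation is below 1, the fixed coefficient leaves avoidable noise in the comparison. Section 7.2 says that the sample is limited to the students at one school, so the choice of model is one of the few ways left to gain power.

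The second is pre-specification. Section 7.1 contains two branches that depend on the data: t-test or non-parametric test, and linear or quantile regression. A further trigger, observed imbalance, decides whether to adjust at all. Thresholds and covariates are not fixed. The methods summarise different things (means, ranks, medians), so the branch taken changes both the p-value and the quantity being estimated. A protocol may leave detail to a later plan. Here, however, the protocol itself makes the choice of primary analysis depend on the trial data.

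**Working it through.** **Inputs.** From the protocol: 50 per arm, alpha 0.05, 80% power, detectable differences 1.52 and 3.58. Assumed because not given: a two-sided test, equal pre and post SDs, no dropout, and r between 0.3 and 0.9.

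**1. The protocol's own figures.** Detectable difference = SD × (1.960 + 0.842) × √(2/50) = SD × 0.560. No SD is printed, so the figures can only be solved backwards: 1.52/0.560 gives an SD of about 2.71 for KAS, and 3.58/0.560 gives about 6.39 for EHI. Both correspond to a standardised difference of 0.56. They agree with each other but cannot be verified.

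**2. Efficiency of ANCOVA against the change score.** Relative to the variance of a single post score, the residual variance is 2(1−r) for the change score and 1−r² for ANCOVA. The ratio is 2(1−r)/(1−r²) = 2/(1+r). Where the change-score test has 80% power, ANCOVA has power Φ(2.802 × √(2/(1+r)) − 1.960). The cost of one degree of freedom is ignored.

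| r | 2/(1+r) | Extra students the change score needs for equal precision | ANCOVA power |
|---|---|---|---|
| 0.4 | 1.43 | 43% | 92% |
| 0.6 | 1.25 | 25% | 88% |
| 0.8 | 1.11 | 11% | 84% |
| 0.9 | 1.05 | 5% | 82% |

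**3. Link to the stated power.** Suppose that the literature SDs in Section 7.2 are for a single time point (not stated). The detectable difference is then the printed figure times √(2(1−r)) for the change score and times √(1−r²) for ANCOVA.

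| r | KAS, change / ANCOVA | EHI, change / ANCOVA | Power at the printed difference, change / ANCOVA |
|---|---|---|---|
| 0.3 | 1.80 / 1.45 | 4.24 / 3.42 | 66% / 84% |
| 0.5 | 1.52 / 1.32 | 3.58 / 3.10 | 80% / 90% |
| 0.6 | 1.36 / 1.22 | 3.20 / 2.86 | 88% / 94% |
| 0.9 | 0.68 / 0.66 | 1.60 / 1.56 | above 99% / above 99% |

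Since 2(1−r) ≤ 1 only when r ≥ 0.5, the planned test reaches the stated 80% only from r = 0.5 upwards. ANCOVA reaches it at any r.

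**4. Type I error.** In null simulations with 50 per arm, each fixed method held about 0.045 to 0.050. Two ways of using the options were compared:
- *Followed as a rule* (6,000 runs, r 0.4 to 0.9, normal and skewed data). The t-test, replaced by Mann-Whitney when a Shapiro test gave p < 0.05, had 0.045 to 0.053. Adding a switch to ANCOVA when the standardised baseline difference exceeded 0.2 gave 0.035 to 0.049. Both thresholds are assumptions, and quantile regression was not simulated.
- *Used as a menu* (4,000 runs). Reporting the smallest p of t-test, Mann-Whitney and ANCOVA gave 0.078 at r = 0.5 and 0.066 at r = 0.8. This is a worst case that the protocol does not propose.

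**The case against.** The strongest reply is that the planned test is sound and the gain may be slight. The same questionnaires are repeated within one 45 to 50 minute period, so r may well be high. At 0.9 ANCOVA lifts 80% power only to 82%. With single-time-point SDs and r above 0.5, the change-score test does better than Section 7.2 claims. Covariate names and normality criteria are also often left to a statistical analysis plan, and Section 7.1 already includes adjusted regression. All of this stands, and it limits the size of the point. It does not supply a single primary analysis.

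A reader might also infer more than the document supports:
- *The 5% level is invalid.* The simulated rules kept about 5% or fell below it. Inflation appears only if the most favourable result is picked.
- *Sections 3.1 and 7.1 target different effects.* Under randomisation, the post score and the change score have the same expected difference between arms. With the baseline score in the model, the arm coefficient is identical for either outcome.
- *Regression to the mean biases the t-test.* It matters conditionally on a chance baseline imbalance; over randomisation the estimate is unbiased.
- *Leaving out classroom is an error.* Omitting a balanced allocation stratum is valid and usually slightly conservative.

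**Conclusion.** The point holds as one of efficiency and pre-specification, and a change should be made. The planned t-test is valid, but ANCOVA on the already collected baseline score has smaller variance for any r below 1. The gain runs from 12 power points at r = 0.4 to 2 at r = 0.9, given equal pre and post SDs, and confidence in its size is only moderate because r is not given. The shortfall against the stated 80% power arises only if r is below 0.5 and the SDs behind 1.52 and 3.58 are for a single time point. Whatever r is, the protocol does not fix which p-value is primary or whether it concerns means, ranks or medians. That is a risk of discretion, not a demonstrated inflation of type I error.

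**What to change.** In Section 7.1, name one primary model for each total score: linear regression of the post score on arm and the baseline score of the same scale, with heteroscedasticity-robust standard errors, used regardless of observed imbalance or normality. Delete the imbalance-triggered adjustment. Keep the change-score t-test, the rank test and quantile regression as named sensitivity analyses. State in Section 7.2 the SDs used, whether they are for one time point or for change, and the r assumed.

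The cost is protocol wording, submitted to the ethics board as an amendment, and one Stata command per scale. Grade is already collected and can be added as a covariate without further data. Classroom, the allocation stratum, is optional. It needs a class code on the study ID, which with age, gender and grade among about 100 students makes individuals easier to identify. That must be weighed against the anonymity promised to students in Section 3.2 and cleared with the ethics board before data collection.

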consequences and a higher risk of substance use disorders⁷. Additionally, peer pressure Ethics ID: REB23-1437 Date: 1/11/2024 and the desire to fit in or try new trends contribute to the likelihood of children and adolescents engaging in vaping⁸. Furthermore, the easy accessibility of e-cigarettes, both online and in retail settings, allows young individuals to obtain them despite age restrictions⁴.

Misinformation surrounding vaping is a pervasive issue, contributing to its uptake among youth. Misinformation may downplay the risks associated with vaping and be partly responsible for the recent youth vaping epidemic^{15,16,17}. Increasing perceived risk, making these risk perceptions more accurate, and lowering misinformation regarding vaping can reduce youth vaping-associated harm^{17,18}. Therefore, effective public health interventions must be developed for youth to increase perceived risk and lower misinformation. The lack of evidence-based vaping cessation interventions is a concern, and leveraging social media for smoking cessation interventions has been proposed as a viable strategy, given its widespread use among young individuals¹⁸. Interventions observed have primarily been public education and school-based efforts, along with community-based interventions, healthcare provider interventions, aerosol-free policies, age restrictions, and advertising and promotion restrictions¹⁹. This multifaceted challenge requires a concerted effort from public health authorities, educators, parents, and the community at large to mitigate the adverse effects of vaping, particularly among the vulnerable youth demographic.

2 Trial Objectives

- To evaluate the grade 7 and 8 students' attitudes about vaping using the Knowledge and Attitudes regarding e-cigarette ingredients, safety, and addictive properties survey and Harm Perception and Reduction Items survey at baseline (before intervention) and immediately after the intervention.
- To determine student opinions regarding the intervention using the *Video Survey* (appendix) after the viewing.

Other objectives

- To inform on if future substance abuse interventions should involve more or less youth engagement.

3 Trial Design

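### The all-items analysis in section 7.1 names no comparison group, so for at least 14 KAS and EHI items the only item-level test stated cannot compare the two videos

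*Protocol*

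**What the plan says.** Protocol section 7.1 describes three layers of KAS and EHI analysis.

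- **Primary.** T-tests ask whether the intervention group "had a significant change between pre and post-intervention compared to the comparison group on the KAS and EHI".
- **Nine selected items.** An exploratory analysis asks whether "the intervention group had a significant change between pre and post intervention compared to the comparison group on the KAS questions 1, 3, and 7"; EHI questions 1, 2, 6, 7, 11 and 13 are handled likewise.
- **All items.** "Further analysis looking at all individual items on the KAS, EHI, and video survey will be done", the purpose being "to explore if the intervention group had a significant change between pre and post intervention and if the personal information collected impacts scores". No comparison group appears in this sentence.

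The Video Survey has its own between-group tests earlier in section 7.1, which ask whether scores "are significantly different between the experimental and comparator groups" on the first five questions, with a Mann-Whitney test on questions 5 and 6.

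Section 3.1 gives individual items a higher standing than section 7.1 does: "The primary endpoints are individual and aggregate item scores on the" KAS and EHI. The objective in the Study Summary is comparative: whether the locally produced video works better than a conventional one made elsewhere.

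**The concern.** The first two layers use almost the same phrase and both end with the comparison group. The third repeats the phrase without it. An analyst who follows the text would run a pre/post significance test in the intervention arm alone.

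That test answers a different question from the trial's. Group B also watches a vaping video (section 3.3) and completes the same questionnaires before and after it, all within a period of about 45 to 50 minutes (section 3.5). Answers may move in both arms because of vaping content in general, or simply because the questions are asked twice. Randomisation removes these influences only when the arms are compared. At stake is a list of significant items that could be credited to the local video when the other video moved them just as much.

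**Working it through.** **1. The plan's own figures.** Section 7.2 states detectable differences of 1.52 (KAS) and 3.58 (EHI) points at 80% power with 50 per arm. No SD is printed, so these cannot be reproduced independently. Solving backwards with SD = difference / [(1.96 + 0.842) × √(2/50)] gives 1.52 / 0.560 = 2.71 and 3.58 / 0.560 = 6.39. These SDs are implied rather than verified. They concern total scores, and nothing below depends on them.

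**2. How many items have no stated between-arm test.**
- Section 7.1 mentions KAS question 10 and EHI question 13, so there are at least 10 + 13 = 23 items.
- Items with a stated between-arm test: 3 (KAS) + 6 (EHI) = 9.
- Remainder: at least 23 − 9 = 14.

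**3. What a within-arm test does when the videos are equally effective.** Inputs are 50 per arm (section 7.2) and alpha 0.05 (section 7.3). Two-sided testing and a paired t-test are assumed, since the protocol does not state the sidedness and the sentence names no test. Let d be the change common to both arms, in SDs of the change score. The documents give no value for d, so a range is shown.

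- Within-arm: P(|T| > 2.01), where T is noncentral t with 49 degrees of freedom and noncentrality d × √50.
- Between-arm: the true difference in change is d − d = 0, so the noncentrality is 0 and the test rejects 5% of the time whatever d is.

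| Common shift d | d × √50 | Within-arm test significant | Between-arm test significant |
|---|---|---|---|
| 0 | 0 | 5% | 5% |
| 0.1 | 0.71 | 11% | 5% |
| 0.2 | 1.41 | 28% | 5% |
| 0.3 | 2.12 | 55% | 5% |
| 0.4 | 2.83 | 79% | 5% |
| 0.5 | 3.54 | 93% | 5% |

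A simulation with 40,000 runs per scenario at d = 0.2, 0.3 and 0.5 gave 28.8%, 54.5% and 93.4% within-arm, and 5.1%, 4.9% and 4.9% between-arm.

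**4. Whether the sentence can be carried out for the Video Survey.** Section 3.2 says: "Following the intervention they will be provided with another copy of the KAS and EHI along with the Video Survey". The survey is completed once, after viewing. There is no pre-video score, so the pre/post change in the sentence cannot be computed for it.

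**5. Whether the between-arm test is available.** Section 7.1 creates pre/post differences for items and totals for each participant, hence in both arms. The comparison needs nothing further.

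**The case against.** The strongest reply is that the sentence is shorthand. It opens as further analysis, follows directly on a sentence that names the comparison group, and draws on change scores computed for everyone. Its inclusion of the Video Survey, which has no pre score, also suggests loose drafting. This may well be what happened, and the text does not say that the comparison group is excluded. The correction is needed all the same, because the sentence taken as written leads to the wrong test.

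A reader might go further and infer that the protocol abandons the randomised comparison. It does not. Between-arm tests are stated for the KAS and EHI totals, for nine items and for Video Survey questions 1 to 6.

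A reader might also infer that the items, being primary endpoints, put the primary result at risk. Section 3.1 does list them so, but section 7.1 builds its primary analysis on total scores and calls the item work exploratory. That conflict needs resolving; it does not show that the total-score comparison is compromised.

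Section 2 sets an objective of evaluating attitudes "at baseline (before intervention) and immediately after the intervention" with no comparator named, so describing pre/post change serves a stated aim. This supports showing within-arm change, but not using its significance to judge one video against the other.

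Finally, it is tempting to add a multiplicity argument: 23 items at 0.05 give 23 × 0.05 = 1.15 expected false positives if nothing changes. The same figure applies to 23 between-arm tests, so it does not count against the within-arm choice in particular.

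**Conclusion.** The point holds in a limited form. As written, the all-items sentence describes a pre/post test in the intervention group, and for at least 14 KAS and EHI items no other item-level test is stated. Such a test cannot show that one video outperforms the other.

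If the videos are equally effective, it would be significant between 11% and 93% of the time for common shifts of 0.1 to 0.5 SD, against 5% for the between-arm test. Those shifts are assumptions, as are two-sided testing, a paired t-test and all 50 students in the arm being analysed. At small shifts the excess is modest, and with no shift it vanishes.

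A flagged item may truly have changed. The error would lie in crediting that change to the local video over the other, and the protocol does not say that it will do so. The primary total-score analysis stands.

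**What to change.** - Rewrite the sentence as a between-arm comparison for every KAS and EHI item: the difference in change, or the post score adjusted for the pre score, with a 95% confidence interval. Label it exploratory.
- Report within-arm pre/post change descriptively.
- Remove the Video Survey from the pre/post wording; its between-group tests are already described earlier in section 7.1.
- Reconcile the status of individual items, which are primary endpoints in section 3.1 and exploratory in section 7.1.

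The cost is wording and a few lines of analysis code. The data collected, the procedures and the sample size stay the same.
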